## **STATISTICAL ANALYSIS**

### **Sample size calculation**

The  $\alpha$  value is set at 0.05 and power of study at 80%. Sample size calculation was based on mean propofol requirement for sedation in a study by Singh T *et al.* We expect a difference of 0.5 mg/kg/hour of propofol between Groups PCS and TCIS.

The sample size was calculated using the 'Power and Sample Size Calculations' program.

Sample size calculated using t- test.

Requested output: Sample size

Independent

Alpha = 0.05; power = 0.8;  $\delta = 0.5$ ;  $\sigma = 0.74$ ; M = 1

Case sample size for t-test = 35

[figure not shown]
Total sample size: 35 x 2 plus 10% drop-out rate = 78

Sample size = 39 per study group.

### **Statistical tests**

Demographic data and total propofol requirement will be analysed using the student's t-test (or Mann Whitney-U test for non-parametric data). Patients' satisfaction score will be compared using the student's t-test. The satisfaction level of anxious patients in PCS group and TCIS group is compared by using the t-test. A p-value  $< 0.05$  will be considered statistically significant.

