### **Inclusion Criteria:**

1. American Society of Anesthesiologists (ASA) I or II.
2. Aged 18-65 years.
3. Elective lower limb orthopaedic surgery under CNB anticipated to last for 1.5 to 2 hours

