### **Exclusion Criteria:**

1. Body Mass Index (BMI)  $> 30\text{kg/m}^2$
2. Unable to cooperate (eg. mental disorders, language barrier)
3. Drug abuse
4. Alcoholism (chronic daily alcohol intake greater than 75 g of pure alcohol for  $\geq 2$  years, where 75g of alcohol = 5 cans of beer, 1 bottle of wine or half a pint of distilled spirit)
5. Contraindications to the study drugs
6. Pregnancy
7. Significant pulmonary or cardiovascular diseases, including Obstructive Sleep Apnoea (OSA) and Obesity Hypoventilation Syndrome (OHS)
8. Features of difficult airway

During the pre-operative visit, the patient will be briefed on the study and informed consent obtained. They will also be assessed for pre-operative anxiety by using the Amsterdam Pre-operative Anxiety and Information Scale (APAIS; Appendix 1), where only the anxiety components of the original questionnaire will be assessed. Patients will be graded on a five-point Likert scale from 1 = not at all, to 5 = extremely anxious. A patient with score  $\geq 11$  is considered anxious.

All patients will be given pre-medication of oral midazolam 3.75 or 7.5 mg accordingly. Subjects will be randomised via computer generated block randomisation into Group PCS and Group TCIS. The study will be conducted by multiple anaesthesia medical officers. In the operating theatre, standard monitoring will include electrocardiogram (ECG), non-invasive blood pressure, pulse oximetry and transthoracic impedance pneumography. Baseline readings will be recorded. Intravenous access will be established with an 18G cannula and normal saline 0.9% infused.

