Central neuraxial block will be performed under aseptic technique by the anaesthesia medical officer in-charge and the L2-3 or L3-L4 intervertebral space sought with the patient sitting. The subarachnoid space will be located using a pencil 27G (B Braun, Germany) spinal needle and hyperbaric bupivacaine 0.5% plus fentanyl 15-25 µg will be administered. In the case of combined spinal-epidural anaesthesia (CSE), the epidural space will be located with a Tuohy 18G epidural needle, and the epidural catheter secured in place (Espocan®, B Braun, Germany). After establishing an adequate sensory level, surgery will be allowed to proceed, and PCS or TCIS commenced. Patients with failed subarachnoid block or sensory block inadequate for surgery will be dropped out from the study. All patients will receive oxygen supplement of 5L/min via a face mask. Heart rate (HR), blood pressure (BP), oxygen saturation (SpO2) and respiratory rate (RR) will be monitored and documented every 5 minutes. Patients will be kept warm with standard intra-operative warming devices during the surgery.

Propofol will be premixed with lignocaine where 10 mg of lignocaine will be added to every 100 mg propofol 1% to reduce the intensity of pain on injection with propofol. Patients in Group PCS will receive intravenous (IV) propofol (Lipuro® 1%, B.Braun, Germany) via a Graseby® Omnifuse patient controlled analgesia (PCA) (Smith's Medical, UK) infusion pump. The machine will be set to deliver a demand bolus dose of 0.25 mg/kg with no lockout interval or basal infusion. The patient will be instructed to press on a hand-held device as often as required to achieve their desired level of comfort or sedation. The sedation level will be assessed using the Observer's Assessment of Alertness/Sedation Scale (OAA/S; Appendix 2) every 5 minutes in the first 30 minutes, followed by every 20 minutes thereafter.

Patients in Group TCIS will receive IV propofol (Lipuro® 1%, B.Braun, Germany) via a Graseby® Omnifusion target-controlled infusion (TCI) pump (Graseby Medical, Watford,

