U.K) targeting an initial effect site concentration (Cet) of 0.6 µg /ml, using the Schnider pharmacokinetic model. Upon attainment of 0.6 µg /ml Cet, the patient's sedation level will be assessed. The Cet will be increased or reduced accordingly by 0.2 µg/ml to attain an OAA/S score of 3. After equilibrium between predicted and set concentration is achieved, OAA/S score is re-assessed and adjustment of Cet is made until OAA/S score of 3 achieved. The induction time, which is the time taken to reach OAA/S of 3, will be documented in both groups. Thereafter the OAS/S will be assessed every 20 minutes.

Complications from sedation will be managed as follows:

1. Hypotension (systolic BP 20% below baseline) will be treated with administration of IV fluid and titrated bolus doses of IV ephedrine 6 mg or IV phenylephrine 100 µg as required.
2. Bradycardia (HR < 40bpm) will be treated with IV atropine 0.6mg.
3. Respiratory depression (RR < 8 breaths/min) and oxygen desaturation (SpO2 < 95%) will be managed by verbal or tactile stimuli, and titrating down Cet by 0.2 µg/ml in the TCI group, delivering 100% oxygen by applying airway maintenance manoeuvres and assisted ventilation as necessary.
4. Over-sedation (OAS/S score ≤ 2) will be managed by verbal or tactile stimuli, and titrating down Cet by 0.2 µg/ml.

The use of airway adjuncts or intubation will be considered depending on the severity of respiratory compromise. These patients will be excluded from analysis of recovery characteristics.

Sedative administration will be terminated (T0) at the completion of surgery. At the recovery area, standard monitoring will be employed. The medical officer in the recovery room will assess the OAS/S score every 5 minutes. The recovery time, which is the time taken to reach OAS/S 5 from T0 will be documented. Total propofol requirement in both groups will be calculated in mg/kg/hour.

Before discharge from the recovery room, patient satisfaction with sedation was measured using a 10-point verbal rating scale, 1 being extremely dissatisfied and 10 being extremely satisfied.

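### The primary propofol comparison is valid but leaves age and APAIS score unused; a prespecified adjusted mean difference with 95% CI is a cheap, optional improvement

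*Combined protocol and SAP*

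**What the plan says.** - **Outcome.** Materials and Methods (the text after the exclusion criteria): "Total propofol requirement in both groups will be calculated in mg/kg/hour".
- **Sizing.** Sample size calculation: "We expect a difference of 0.5 mg/kg/hour of propofol between Groups PCS and TCIS", with SD 0.74, alpha 0.05 and 80% power. This gives 35 per arm, raised to 39 per arm (78 in total) for 10% drop-out.
- **Primary analysis.** Statistical tests: "total propofol requirement will be analysed using the student's t-test (or Mann Whitney-U test for non-parametric data"). The section sets a significance threshold of p < 0.05. It names no between-arm difference, confidence interval or covariate, and no criterion for moving from the default test to the fallback.
- **Age.** The inclusion criterion is "Aged 18-65 years", and age is a field on the data collection form.
- **Anxiety.** At the pre-operative visit, "They will also be assessed for pre-operative anxiety by using the Amsterdam Pre-operative Anxiety and Information Scale". The score enters the planned analysis only through the comparison of satisfaction among anxious patients (score 11 or more). It has no role in the propofol comparison.

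**The concern.** Both baseline values are fixed before surgery, so they can enter the primary model without introducing bias. If they are related to propofol requirement, leaving them out makes the interval for the treatment difference wider than it need be. The trial has little room for this, because power for the t-test is just under 80% with 35 per arm.

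Separately, the trial is sized on a mean difference of 0.5 mg/kg/hour, but the analysis text commits only to a test. A p-value alone would not tell a reader how large the difference is, or how precisely it is known, on the scale on which the trial was designed.

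**Working it through.** **Inputs from the documents.** Difference 0.5 mg/kg/hour, SD 0.74, alpha 0.05, power 80%, equal arms, 35 evaluable per arm, 39 randomised per arm. Sidedness is not stated. Two-sided is assumed because it returns 35, whereas one-sided gives 28.

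**Assumed input.** R², the share of within-arm variance in propofol dose explained by age and APAIS together. The documents give no value, so a range of 0 to 0.30 is shown.

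**1. The plan's own figure.** n = 2(1.960 + 0.842)² × 0.74² / 0.5² = 2 × 7.849 × 0.5476 / 0.25 = 34.4, so 35 per arm. For drop-out, 70 / 0.9 = 77.8, so 78. Both match. The exact t calculation gives 35.4 per arm, which is why power below is slightly under 80%.

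**2. Unadjusted t-test, 35 per arm.** SE = 0.74 × √(2/35) = 0.1769, with 68 df. Noncentrality is 0.5 / 0.1769 = 2.827. Power is 79.6%. The 95% CI half-width is 1.995 × 0.1769 = 0.353.

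**3. Adjusted for two covariates, 35 per arm.** SE = 0.74 × √(1 − R²) × √[(2/35) × 67/65], with 66 df. The factor 67/65 pays for chance imbalance in two covariates. Half-width = 1.997 × SE.

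| R² | SE | Noncentrality | Power | Half-width (mg/kg/hour) |
|---|---|---|---|---|
| 0 | 0.1796 | 2.784 | 78.3% | 0.359 |
| 0.05 | 0.1750 | 2.856 | 80.4% | 0.349 |
| 0.10 | 0.1704 | 2.935 | 82.4% | 0.340 |
| 0.20 | 0.1606 | 3.113 | 86.6% | 0.321 |
| 0.30 | 0.1503 | 3.328 | 90.6% | 0.300 |

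Adjusted power equals unadjusted power at R² = 0.031.

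**4. If all 39 per arm are analysed.** Unadjusted power is 83.8%. Adjusted power is 82.8, 84.6, 86.5, 90.1 and 93.5% at the same R² values, with break-even at 0.027.

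**5. APAIS acting differently by arm.** This was simulated with normal errors, 35 per arm and 10,000 trials per cell (simulation error about 0.4 points).
- APAIS explains 10% of variance in the patient-controlled (PCS) arm only, age nothing: 79.9% adjusted v 80.0% for the t-test. If APAIS does so in both arms, adjusted power is 82.9%.
- APAIS explains 10% with opposite sign in the two arms: 78.8% v 80.4%.

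Regression type I error was 4.7 to 5.4% in these cells.

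**6. Against the Mann-Whitney fallback.** Same simulation size, gamma errors equally skewed in both arms, shift of 0.5. Entries are Mann-Whitney v adjusted regression power (%).

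| Skewness | R² = 0 | R² = 0.10 | R² = 0.20 |
|---|---|---|---|
| 1 | 84.6 v 78.7 | 82.9 v 82.2 | 81.7 v 86.7 |
| 1.5 | 90.7 v 78.6 | 88.7 v 82.7 | 85.6 v 86.6 |
| 2 | 96.0 v 78.6 | 93.0 v 82.3 | 89.6 v 86.4 |

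With clear skewness and a low R², the planned fallback has more power than the linear model.

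**7. Does the open switch harm type I error?** This was simulated with 20,000 runs and both arms sharing one distribution. Switching on a Shapiro test gave 5.0 to 5.2%, against 4.9 to 5.0% for either test alone. That is no material inflation.

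**The case against.** **The plan contains no error.** This stands. An unadjusted two-sample comparison is standard in a randomised trial, and the sample size is right.

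**The gain has no basis in the documents.** This also stands. No section relates age or APAIS to propofol dose, and there are reasons to doubt APAIS in particular. Patients in the PCS arm "press on a hand-held device as often as required to achieve their desired level of comfort or sedation", whereas in the target-controlled arm "adjustment of Cet is made until OAA/S score of 3 achieved", so anxiety may bear on dose in one arm more than in the other. Also, "All patients will be given pre-medication of oral midazolam 3.75 or 7.5 mg accordingly", which may blunt any anxiety effect. Hence the range from R² = 0.

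**A linear model as the only primary analysis can do worse than the plan.** This is the strongest point, and it stands. Against the planned rule with a Shapiro-based switch, at R² = 0, the linear model lost about 5, 12 and 17 power points at skewness 1, 1.5 and 2. It is the reason for keeping the fallback.

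**Stronger readings that the documents do not support.**
- A reader might infer that no test was chosen in advance. A default and a fallback are both named; only the criterion for switching is missing.
- A reader might infer that the switch inflates type I error. The figures of 6.0 to 6.7% arise only if the smaller of the two p-values may be taken, which the plan does not allow.
- A reader might infer from the data collection form, which shows no APAIS field, that the score is not captured. The satisfaction comparison in anxious patients already needs it, Appendix 1 holds the items, and the form as extracted also lacks the planned satisfaction score. The form is therefore no evidence either way.

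**The missing estimate is a reporting detail.** Largely fair: the text does not exclude an estimate. A commitment to report one still costs nothing.

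**Conclusion.** Low severity: an optional improvement to a valid plan. With 35 per arm, adjustment changes power relative to the unadjusted 79.6% by about −1 point at R² = 0, +3 at 0.10 and +7 at 0.20. It pays for itself once age and APAIS together explain about 3% of within-arm variance.

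These figures assume a two-sided test, the planning SD of 0.74, roughly normal errors and covariate effects that are similar in both arms. R² itself is not known from the documents. The case for reporting a mean difference with 95% CI in mg/kg/hour does not depend on R².

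**What to change.** Before any outcome data are seen, amend Statistical tests as follows.

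1. Replace the unadjusted t-test with a linear model of propofol mg/kg/hour on arm, age and continuous APAIS score. Robust standard errors are acceptable.
2. Always report the adjusted mean difference with its 95% CI in mg/kg/hour, whichever test supplies the p-value.
3. Keep a rank-based fallback for clearly skewed data: either Mann-Whitney as planned, or a rank analysis adjusted for the same two covariates. State the switching criterion in advance. Mann-Whitney does not test the mean difference when the arms differ in shape, so the text should say which result carries the primary conclusion if the two disagree.
4. State how a missing APAIS score would be handled, for example by filling it with the mean over both arms pooled, so that no analysed patient is lost.

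**Cost.** A few lines of wording and one regression model. No extra patients and no new measurement are needed. The statistical price against the t-test is about 1 power point if the covariates explain nothing.

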Patient-controlled sedation (PCS) is a valid option for surgeries or procedures under regional anaesthesia. It is a well-established technique, initially adapted from post-surgery patient controlled analgesia. First reported in 1991, Rudkin et al studied PCS with propofol in patients undergoing dental extractions under local anaesthesia. Park and Watkins studied the efficacy of anaesthetist-controlled sedation (ACS) versus PCS, both using bolus delivered

midazolam and fentanyl, in patients undergoing lower extremity and lower abdominal procedures under epidural anaesthesia. In both studies, PCS resulted in significant satisfactory response from the patients. In 2000, Girdler et al reported that patients utilizing PCS with propofol reached target sedation faster, though not significant, than patients with ACS of continuous propofol infusion in surgeries under local anaesthesia. In 2008, Wahlen et al reported significantly lower plasma and effect-site propofol concentration with high degree of patient satisfaction among patients on PCS compared to ACS of continuous propofol infusion in patients undergoing total knee and hip replacements under spinal anaesthesia.

This study aims to compare the effectiveness of ACS using TCI sedation (TCIS), versus PCS in patients undergoing lower limb orthopaedic surgery under central neuraxial block (CNB). If PCS could be shown to be superior in terms of reduced propofol requirement, in addition to improved safety, sedation quality and patient satisfaction, it could be an alternative sedation option, or replace ACS as the current means of sedation in surgeries under CNB.

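### Does the t-test of satisfaction in anxious patients need an arm-by-anxiety interaction beside it?

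*Combined protocol and SAP*

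**What the plan says.** The primary objective (Objectives section) concerns total propofol requirement. Satisfaction appears in the secondary objective, together with complications and sedation quality. The Introduction makes it part of the case for patient-controlled sedation (PCS): "in addition to improved safety, sedation quality and patient satisfaction, it could be an alternative sedation option".

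Anxiety is graded at the pre-operative visit with the APAIS, of which "only the anxiety components of the original questionnaire will be assessed". A patient scoring 11 or more "is considered anxious" (Materials and Methods, text after the exclusion criteria). Satisfaction is scored before discharge from recovery on a "10-point verbal rating scale, 1 being extremely dissatisfied and 10 being extremely satisfied".

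Under Statistical tests, the overall "satisfaction score will be compared using the student's t-test". The next sentence is the only subgroup analysis in the plan: "The satisfaction level of anxious patients in PCS group and TCIS group is compared by using the t-test". One rule covers all tests: a p-value below 0.05 "will be considered statistically significant". The plan contains no interaction term, no comparison in non-anxious patients and no exploratory label. The sample size section gives "Case sample size for t-test = 35", before inflation for drop-out.

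**The concern.** A significant result in one set of patients and a non-significant result in another does not show that the effects differ. The anxious subgroup must be smaller than the whole trial, so its test can miss an effect that the overall test detects, even when the effect is the same in everyone. The reverse pattern can also occur by chance.

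The plan names anxious patients as its one subgroup, tests them at the same threshold as the whole sample, and offers no direct estimate of whether anxiety changes the effect. At stake would be an unsupported statement that PCS suits anxious patients better, or worse, than others. The primary endpoint and the sample size would not be touched. A linear model with arm, anxiety and their product would supply the missing estimate at the price of a few lines of SAP text.

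**Working it through.** **1. The plan's own figure.** Inputs from Sample size calculation: α = 0.05, power 80%, δ = 0.5, σ = 0.74, ratio 1:1. Sidedness is not stated; a two-sided test reproduces the figure.

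n = 2[σ(z₀.₉₇₅ + z₀.₈₀)/δ]² = 2[0.74 × (1.960 + 0.842)/0.5]² = 34.4, so 35 per arm. Allowing for drop-out, 70/0.9 = 77.8, so 78. Both match. The figures below use 35 evaluable patients per arm.

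**2. Which question each analysis answers.**

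| Analysis | Quantity | In the plan? |
|---|---|---|
| t-test, all patients | arm effect overall | yes |
| t-test, anxious patients | arm effect among the anxious | yes |
| arm × anxiety term | effect in anxious minus effect in non-anxious | no; no objective asks for it |

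The second row is a sound randomised comparison. The subgroup is defined by a fixed cut-off on a score taken before any sedation, so treatment cannot influence who belongs to it. Randomisation is not described as stratified by anxiety, so the numbers of anxious patients per arm may differ by chance. That costs a little precision but causes no bias.

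**3. How often the two planned tests disagree.** The documents give no anxious share, satisfaction SD or expected satisfaction effect. Assumed: 7, 10 or 14 anxious per arm (20% to 40%), normal scores, and the same effect in everyone. Simulation with 40,000 runs; each cell shows 7 / 10 / 14 anxious per arm:

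| True effect | Tests disagree (%) | Overall significant, anxious not (%) | Anxious significant, overall not (%) |
|---|---|---|---|
| 0.2 SD | 15.1 / 14.4 / 13.3 | 10.9 / 10.1 / 9.2 | 4.3 / 4.3 / 4.1 |
| 0.5 SD | 45.8 / 41.8 / 36.3 | 42.8 / 38.7 / 32.6 | 3.0 / 3.1 / 3.7 |
| 0.8 SD | 64.5 / 52.8 / 39.8 | 63.9 / 52.0 / 38.9 | 0.7 / 0.8 / 1.0 |

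On rounded 1 to 10 scores with 5% low scorers in both arms, disagreement falls to about 11%, 28–23% and 44–35%, and the last column becomes 4.0% to 5.5%. Disagreement is common, but nearly all of it is a smaller subgroup having less power. The pattern most likely to prompt an anxiety-specific claim is rare.

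**4. What an interaction would add.** With a anxious and b non-anxious patients per arm and a common SD, the standard error is SD × √(2/a + 2/b), with 66 degrees of freedom (t = 1.997).

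- a = 7, b = 28: √(0.2857 + 0.0714) = 0.598; half-width 1.997 × 0.598 = 1.19 SD.
- a = 14, b = 21: √(0.1429 + 0.0952) = 0.488; half-width 1.997 × 0.488 = 0.97 SD.

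With separate variances for anxious and non-anxious patients, the half-widths are 1.24 / 1.07 / 0.97 SD for 7 / 10 / 14 anxious per arm. Power to detect a difference in effect of 0.68 SD (0.5/0.74, borrowed from the primary endpoint for illustration) is 19% / 24% / 28%. Such an interval will seldom separate the same effect from a different one.

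**5. Whether the model leaves the planned test intact.** It does so only if the anxious-patient contrast keeps its own variance and its own 2a − 2 degrees of freedom, as a Satterthwaite approximation gives. With the model's 66 residual degrees of freedom, the nominal 5% test in anxious patients has true size 6.9% / 6.1% / 5.6%. Its interval is too narrow by 8% / 5% / 3% (for a = 7, 1.997/2.179 = 0.92).

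**6. Behaviour where it would matter most.** Among simulated trials with the pattern anxious significant, overall not, and no true interaction, the interaction is itself below 0.05 in 62% / 41% / 34% at 0.2 / 0.5 / 0.8 SD with 7 anxious per arm, and in 42% / 32% / 24% with 14. The unconditional false-positive rate is still 5%; the excess comes from looking only at trials with that pattern. In those trials the added analysis would often reinforce the misreading it was meant to prevent.

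**The case for a change.** The best argument for the concern is that readers do compare adjacent p-values, whatever the plan intends. Anxious patients are the only subgroup named, satisfaction is part of the rationale for PCS, and disagreement between the two tests is likely at moderate effects. An interaction estimate with its interval would at least show how little the subgroup can say. Fitted with separate variances and Satterthwaite degrees of freedom, it holds its 5% error rate, reproduces the planned anxious-patient test, and needs no extra patients or data.

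Part of this stands. No interaction is planned, the disagreement rates are right under their assumptions, and an inference from two p-values on opposite sides of 0.05 would be a poor one. But no section makes or announces that inference. The harm depends on a reader drawing a conclusion the plan does not draw. The remedy gives a very imprecise answer to a question outside the objectives, and it gives least protection in the one pattern where protection would be most wanted. A sponsor may add it as an extra. Leaving it out is not a fault.

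**Conclusion.** The concern does not hold. The anxious-only t-test is a pre-defined comparison of randomised arms within a baseline subgroup, and it validly answers the question the plan asks. Whether anxiety modifies the effect is a separate question that neither the objectives nor the statistical section raises. Adding an interaction would change no planned result; it would contribute an interval of about ±1.2 to ±1.0 SD with 19% to 28% power for a 0.68 SD difference. The primary analysis and the 78 patients are unaffected either way.

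The sizes rest on assumed values: 20% to 40% anxious, effects of 0.2 to 0.8 SD, and equal SDs in anxious and non-anxious patients. The conclusion does not rest on them, because it follows from which question the plan sets and which test it uses.
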